Event/ Assessment ^a	Window: Day 1 (±0 days)	Window: Day 8 (±1 day)	Window: Day 15 (±2 days)	Window: Day 22 (±2 days)	Window: Day 36 (±2 days)	Window: Day 64 (±2 days)	Window: Day 92 (-2 days)		Comments
Abbreviated Physical examination	X	X	Х	X	X	X	Х	X	In addition to the scheduled visits, symptom-directed physical examinations will occur at any time during the study if triggered by AEs or if deemed necessary by the investigator (Section 11.6.3).
Serum chemistry	X Fasted	X	X	X Fasted	X	X	X Fasted	X Fasted	A blood sample will be collected predose after an overnight fast on indicated days. All other days do not require fasting. (Section 11.6.2).
Hematology	X	X	X	X	X	X	X	X	A blood sample will be collected (Section 11.6.2).
Coagulation	X	X	X	X	X	X	X	X	A blood sample will be collected (Section 11.6.2).
Biomarker blood sample	X	X	X	X	X	X	X	X	Section 11.5.1.
VX-147 PK blood sample	intensive	predose	intensive	predose	intensive	predose	X	X	A blood sample will be collected (Section 11.2.1). Intensive PK sampling Day 1, Day 15, Week 5: predose (within 60 min before dosing) and 0.25, 0.5, 1, 2, 4 and 12 hours postdose Post treatment samples (Week 13 and ETT): A single sample collected anytime during the Visit.

Protocol VX19-147-101, Version 6.0

Table 3-2 Study VX19-147-101: Part A Treatment Period 1, Treatment Period 2, and Early Termination of Treatment Visit

	Treatmen	t Period 1 Treatment Period 2					 		
	Day 1 Visit	Week 1 Visit	Day 15 Visit	Week 3 Visit	Week 5 Visit	Week 9 Visit	Week 13 Visit	Early	
Event/ Assessment ^a	Window: Day 1 (±0 days)	Window: Day 8 (±1 day)	Window: Day 15 (±2 days)	Window: Day 22 (±2 days)	Window: Day 36 (±2 days)	Window: Day 64 (±2 days)	Window: Day 92 (-2 days)	Termination of Treatment Visit ^b	Comments
Urine sample β-hCG (urine)	Х°	X	X	X	X (3 samples)	X (3 samples)	X (3 samples)	X	The first morning urine void (predose) will be collected and used for efficacy, safety, and biomarker analyses (Sections 11.3 and 11.6.2). During Week 5, Week 9, and Week 13, 3 samples will be collected on 3 separate days within a 7-day period. If the subject forgets to collect the first morning void on the day of the visit, they may provide this sample predose on a different day within the visit window. Refer to sample handling guidelines to ensure samples are submitted appropriately for analysis. All female subjects of childbearing potential

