Standard 12-lead ECG		X		Complete after SF-36 and before other assessments after subject has been supine for at least 5 minutes. ECGs (Section 11.6.4), vital signs, and blood draws should be performed in said order.
Vital signs		X		Complete before other assessments listed below after subject has been at rest for at least 5 minutes; they should be seated during the assessment (Section 11.6.3). Blood pressure will be collected in triplicate.

^a The postdose PK sampling visit is required for all subjects, with the exception of those who complete an ETT Visit.

The SFUV and Part B Week 4 Off-treatment Follow-up Visit may occur on the same day, provided the visit windows are met for both visits.

Visit windows for Part B are as follows: Week 4 Visit (Day 120 ± 2 weeks), Week 8 Visit (Day 148 ± 2 weeks), Week 12 Visit (Day 176 ± 2 weeks).

Table 3-3 Study VX19-147-101: Postdose PK Sampling, Safety Follow-up Visit, and Part B Off-treatment Follow-up Period

On-treatment Follow-up reriou					
Event/Assessment	Postdose PK Sampling (Approximately 48 hours after the last dose of study drug) ^a	SFUV 28 (± 7) Days After Last Dose of Study Drug ^b	Part B: Optional Off-treatment Follow-up Visits (Part B Week 4 ^b , 8, and 12)	Comments	
Weight		X		Weight will be measured with shoes off and light weight closing (no outerwear). (Section 11.1).	
Abbreviated physical examination		X		In addition to the scheduled visits, symptom-directed physical examinations will occur at any time during the study if triggered by AEs or if deemed necessary by the investigator (Section 11.6.3).	
Serum chemistry		X Fasted		A blood sample will be collected following an overnight fast (Section 11.6.2).	
Hematology		X		A blood sample will be collected (Section 11.6.2)	
Coagulation		X		A blood sample will be collected (Section 11.6.2)	
VX-147 PK Sampling	X			A blood sample will be collected (Section 11.2.1).	
Urine sample		X	X	The first morning urine void will be collected and used for efficacy, safety, and biomarker analyses (Sections 11.3 and 11.6.2). Refer to sample handling guidelines to ensure samples are collected and submitted appropriately for analysis.	
β-hCG (urine)		X		All female subjects of childbearing potential (Section 11.6.2). This can be collected in the same sample as the other urine sample.	
Adverse events		gning of ICF through UV	NA	Section 11.6.1	

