9 STATISTICAL ANALYSIS

9.1 General Considerations

The Schedule of Assessments is provided in Section 3 of the CSP. The precision standards for reporting variables are provided in an internal Biometrics document that specifies the programming rules including the precision for derived variables.

Continuous variables will be summarized using the following descriptive summary statistics: the number of subjects (n), mean, SD, median, minimum value (min), and maximum value (max).

Categorical variables will be summarized using counts and percentages.

Baseline value, unless specified otherwise, will be defined as the most recent non-missing measurement (scheduled or unscheduled) collected before the first dose of study drug in the Treatment Period. For ECGs, baseline will be defined as the most recent pretreatment measurement (or the average of triplicate measurements, if the most recent pretreatment measurement is obtained in triplicate) before the first dose of study drug in the Treatment Period. For systolic and diastolic blood pressure, baseline will be defined as the most recent pretreatment measurement (or the average of triplicate measurements, if the most recent pretreatment measurement is obtained in triplicate) before the first dose of study drug in the Treatment Period. For UPCR (and UACR) data baseline value will be the average of UPCR (UACR) values from the 3 urine samples collected during screening for the purpose of assessing eligibility.

Change (absolute change) from baseline will be calculated as Post-baseline value – Baseline value.

Treatment-emergent (TE) Period will include the time from the first dose of study drug in the Treatment Period to either (1) the Safety Follow-up Visit, (2) ETT Visit if it replaces the Safety Follow-up Visit, or (3) the date of the last dose + 28 days for subjects who do not have a Safety Follow-up Visit. The TE Period will be used for safety analyses unless specified otherwise.

Unscheduled visits: Data obtained from unscheduled visits will be included in the analysis as follows:

- In scheduled visit windows per specified visit windowing rules
- In the derivation of baseline
- In the derivation of maximum and minimum values during TE period, and maximum and minimum change from baseline values during TE period for safety analyses
- In individual subject data listings as appropriate

Visit Window: The analysis visit windows for the protocol-defined visits are provided in [Appendix A](#).

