9.3.2 Analysis of Exploratory Efficacy Variables

9.3.2.1 Definition of Exploratory Efficacy Variable

UPCR (and UACR) values at Week 5, Week 9 and Week 13 will be calculated as the average of the available UPCR (and UACR) measurements (maximum 3) taken during Week 5, Week 9 or Week 13 within a 7-day period as described in [Appendix A](#).

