9.3.2.2 Analyses of Exploratory Efficacy Variable

Percent change from baseline in UPCR over time during the Treatment Period: Analysis of this variable will be based on steps as described for primary analyses in Section 9.3.1.2. Subjects non-compliant with study drug will not be included in the analysis. The GMPC from baseline in UPCR, GSE (%) along with the corresponding 2-sided 80% CI and 95% CI at each post-baseline visit (Week 1, Day 15, Week 3, Week 5, Week 9, and Week 13) will be provided. The GMPC from baseline in UPCR at each post-baseline visit during the Treatment Period will also be presented in a figure.

Percent change from baseline in urine albumin-to-creatinine ratio (UACR) at Week 13: Analysis of this variable will be conducted in the same way as described for primary analyses Section 9.3.1.2. Subjects non-compliant with study drug will not be included in the analysis. The GMPC from baseline in UACR at Week 13, GSE (%) along with the corresponding 2-sided 80% CI will be provided.

Percent change from baseline in UACR over time during the Treatment Period: Analysis of this variable will be based on steps as described for primary analyses in Section 9.3.1.2. Subjects non-compliant with study drug will not be included in the analysis. The GMPC from baseline in UACR, GSE (%) along with the corresponding 2-sided 80% CI at each post-baseline visit (Week 1, Day 15, Week 3, Week 5, Week 9, and Week 13) will be provided. The GMPC from baseline in UACR at each post-baseline visit during the Treatment Period will also be presented in a figure.

Percent change from baseline in UPCR at the end of the Off-treatment Follow-up Period: Analysis of this variable will be based on steps as described for primary analyses in Section 9.3.1.2. Subjects non-compliant with study drug will not be included in the analysis. The GMPC from baseline in UPCR, GSE (%) along with the corresponding 2-sided 80% CI and 95% CI at each visit in Off-treatment Follow-up Period (Part B Week 4, Week 8, and Week 12) will be provided. The GMPC from baseline in UPCR at each post-baseline visit during the Off-treatment Period will also be presented in a figure.

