12 APPENDICES

Appendix A: Analysis Visit Windows for Efficacy, Safety, and Exploratory Assessments

Table 12-1 Analysis Visit Windows for Efficacy, Safety, and Exploratory Assessments			
Assessment	Visit¹	Target Study Day	Analysis Visit Window (in study days)^{2, 3, 4, 5}
Efficacy Assessments			

 • UPCR 	Baseline	Not applicable	<1
	Week 1	8	(1, 11]
	Day 15	15	(11, 18]
	Week 3	22	(18, 29]
	Week 5	36	(29, 50]
	Week 9	64	(50, 78]
	Week 13	92	(78, 106]
	Part B Week 4	120	(106, 134]
	Part B Week 8	148	(134, 162]
Part B Week 12	176	(162, 190]	

 • UACR 	Baseline	Not applicable	<1
	Week 1	8	(1, 11]
	Day 15	15	(11, 18]
	Week 3	22	(18, 29]
	Week 5	36	(29, 50]
	Week 9	64	(50, 78]
	Week 13	92	(78, 106]
Safety Assessments			

 • Serum Chemistry • Hematology • Coagulation 	Baseline	1	≤1 Pre-dose
	Week 1	8	[1 Post-dose, 11]
	Day 15	15	(11, 18]
	Week 3	22	(18, 29]
	Week 5	36	(29, 50]
	Week 9	64	(50, 78]
	Week 13	92	(78, 106]
	Safety Follow-up	Not applicable	Use nominal visit

 • Standard 12-lead ECG 	Baseline	1	≤1 Pre-dose
	Day 1 (2 hours post dose)	1	Nominal visit for all visits
	Week 1	8	
	Day 15 predose	15	
	Day 15 (2 hours post dose)	15	
	Week 3	22	
	Week 5	36	
	Week 9	64	
	Week 13	92	
	Safety Follow-up	Not applicable	

 • Vital Signs • Weight 	Baseline	1	≤1
	Week 1	8	[1 Post-dose, 11]
	Day 15	15	(11, 18]
	Week 3	22	(18, 29]
	Week 5	36	(29, 50]
	Week 9	64	(50, 78]
	Week 13	92	(78, 106]
	Safety Follow-up	Not applicable	Use nominal visit
Exploratory Assessments			

 • SF-36 	Baseline	1	≤1
	Week 5	36	[1 Post-dose, 64]
	Week 13	92	(64, 106]
	Safety Follow-up	Not applicable	Use nominal visit

Notes:

¹Visit name for analysis purpose is used to report data in tables and figures.

²The analysis visit windows will be applied using the following rules for both scheduled and unscheduled visits:

- a. If no numerical measurement is available within a visit window, the measurement will be considered missing for the visit.
- b. If there is more than 1 numerical measurement available within a visit window, use the following rules:
 - i. The measurement closest to the target day will be used; or

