 - ii. If there are multiple measurements with the same distance from the target day, the latest measurement will be used. If the latest measurement cannot be determined, then unscheduled visit will be selected.
 - iii. If there are multiple measurements from the central laboratory and local laboratory with the same distance from the target day, the measurement from the central laboratory will be used.

³For measurements collected on the date of first dose of study drug in Treatment Period, if it cannot be determined whether the measurement is before or after the first dose:

- a. Scheduled measurement will be treated as pre-dose observation;
- b. Unscheduled measurement will be treated as post-dose observation.

⁴For safety assessment, the Safety Follow-up analysis visit will be based on nominal Safety Follow-up visit. If a subject doesn't have a nominal Safety Follow-up visit but has an ETT visit occurs 3 weeks (21 days) or later following the last dose of study drug, then the ETT visit will be mapped into Safety Follow-up analysis visit.

⁵UPCR and UACR at Week 5, Week 9 and Week 13 will be calculated by averaging maximum 3 nonmissing UPCR and UACR values measured within a 7-day period within the visit window.

- a. If there is only 1 assessment within the visit window, use the single value
- b. If there are more than 1 assessment within the visit window:
 - i. find the earliest assessment within the visit window, and then find the number of assessments within 7 days after the earliest assessment;
 - ii. find the second assessment within the visit window, and then find the number of assessments within 7 days after the second assessment;
 - iii. find the third assessment within the visit window, and then find the number of assessments within 7 days after the third assessment, if applicable;
 - iv. Compare the number of assessments from step i to iii, use the assessments from the step that has the maximum number. If number of assessments are the same from multiple steps, then use the step with the first assessment closest to target study day.

Derived Variable:

1. Missing first dose date or last dose date
 - If the first dose date is missing, use Day 1 visit date to impute.

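### Do single-sample visits read low enough against three-sample visits in the UPCR and UACR time courses to require a change?

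*SAP*

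**What the plan says.** Protocol Version 6.0, Table 3-2, sets the sampling in Part A: "During Week 5, Week 9, and Week 13, 3 samples will be collected on 3 separate days within a 7-day period". Week 1, Day 15 and Week 3 have one sample each. Table 3-3 gives one void per Part B visit: "The first morning urine void will be collected and used for efficacy, safety, and biomarker analyses".

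SAP 9.1 defines baseline as the "average of UPCR (UACR) values from the 3 urine samples collected during screening for the purpose of assessing eligibility". SAP 9.3.2.1 has the later three-sample values "calculated as the average of the available UPCR (and UACR) measurements (maximum 3) taken during Week 5, Week 9 or Week 13". For Weeks 5, 9 and 13, Appendix A note 5 says the value "will be calculated by averaging maximum 3 nonmissing UPCR and UACR values measured within a 7-day period within the visit window". At the other visits note 2b selects one value if several fall in the window: "The measurement closest to the target day will be used".

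SAP 9.3.1.1 defines the Week 13 value as an average, and 9.3.1.2 then logs the UPCR values and takes the mean change from baseline. The order is not spelled out, but average-then-log is the natural reading, and Protocol 12.3.3.1 reads the same way.

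SAP 9.3.2.2 reports the Part A geometric mean percent change (GMPC) "at each post-baseline visit (Week 1, Day 15, Week 3, Week 5, Week 9, and Week 13) will be provided", with a figure. The Part B UPCR result is reported "at each visit in Off-treatment Follow-up Period (Part B Week 4, Week 8, and Week 12) will be provided", with its own figure, and SAP 9.3 places it on the Follow-up Set. UACR has no Part B analysis.

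**The concern.** The logarithm is concave, so the log of an arithmetic mean of three variable readings is on average higher than the log of one such reading. At Weeks 5, 9 and 13 the same upward term sits in the visit value and in baseline, and it cancels. At a single-void visit it sits only in baseline, so the GMPC comes out too low relative to the three-void visits. More subjects do not remove this, and the confidence interval does not reflect it.

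The Part A table and figure run from one-void to three-void visits without marking the change. Protocol 9.3.3 gives the early readings a purpose: the 15 mg period is meant to show whether proteinuria falls measurably within two weeks. An offset that slightly enlarges the early fall, and slightly shrinks the further fall to Weeks 5 to 13, would matter if it were large. Likewise, any Part B comparison with on-treatment Weeks 5 to 13 would slightly understate a rebound.

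**Working it through.** **Inputs.** SD of log change 0.672, n = 10 and 80% half-width 0.294 (SAP 7.2; Protocol 12.1). Void counts per visit come from Tables 3-2 and 3-3. Protocol 9.3.4.1 says that UPCR varies within a person but gives no figure, so CVs of 20%, 30% and 40% are assumed.

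**1. The plan's own figure.** t(0.90, 9 df) × 0.672/√10 = 1.383 × 0.2125 = 0.294. It reproduces.

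**2. Size of the shift.** For lognormal voids with log variance s² = ln(1 + CV²), the expected log of a k-void mean exceeds that of a single void by about (s²/2)(1 − 1/k). With k = 3 this is s²/3, and the relative shift of a single-void visit is exp(−s²/3) − 1. The last two columns are simulated.

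| CV | s² | s²/3 | Formula | Independent voids | Half the variance shared in the week |
|---|---|---|---|---|---|
| 20% | 0.0392 | 0.0131 | −1.30% | −1.30% | −0.65% |
| 30% | 0.0862 | 0.0287 | −2.83% | −2.79% | −1.42% |
| 40% | 0.1484 | 0.0495 | −4.83% | −4.72% | −2.41% |

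Gamma-distributed voids at CV 30% give −0.031 log units, so the result does not hinge on the lognormal shape. Two voids against three give −0.33%, −0.72% and −1.24%.

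**3. Selection on baseline.** The baseline voids also decide eligibility. Simulating selection on the two cohort bands with no true change (assumed population medians of 3 or 5 g/g for Cohort 1 and 1.5 or 2.5 g/g for Cohort 2; between-subject log SD 0.5 or 0.8) leaves the one-against-three contrast at −1.3%, −2.8% and −4.7%. Selection itself moves the three-void GMPC by −3.3% to +4.1% at CV 30%. Averaging logs leaves that almost unchanged, at −3.2% to +3.9%. It is a separate matter from void count.

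**4. Scale.** The shift is 0.013, 0.028 and 0.048 log units. Divided by 0.294, that is 4%, 10% and 16% of the planned Week 13 half-width. This is for scale only, since no SD is given for single-void visits.

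**5. Primary endpoint.** With three voids at both times the terms cancel. If one subject has a single Week 13 void at CV 40%, the GMPC moves by 0.048/10 = 0.0048 (−0.5%) at n = 10, or 0.048/20 = 0.0024 (−0.2%) at n = 20.

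**6. What the repair would do.** Averaging logged voids brings the contrast to within 0.1 percentage point of zero with no loss of precision: at CV 40% the SD of a three-void visit value is 0.222 for the mean of logs and 0.228 for the log of the mean. It also lowers each subject's baseline on average by 2.8% (CV 30%) or 4.7% (CV 40%). The per-subject difference between the two Week 13 definitions has mean zero and SD 0.040 (CV 30%) or 0.067 (CV 40%). Dividing by √20 gives 0.9% and 1.5%; by √10, for one cohort, 1.3% and 2.1%. The observed primary would move by amounts of that order in either direction.

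**The case for a change.** The best case for a change is that this is a systematic offset with a known direction, in a figure that readers will use to compare early with late visits. The remedy needs no new data, and a footnote costs one line. The direction and the arithmetic stand, as does the remark that the order of averaging and logging is left implicit.

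Several things limit its reach.

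- Only the Part A curves mix void counts. Every Part B visit has one void, so the shape of the Part B curve is unaffected; the offset there is against the shared baseline and the Part A three-void visits. That comparison is not like for like anyway: under Protocol 9.1.3 Part B is optional, and both entry and stopping depend on UPCR relative to 90% of baseline.
- Day 15 against Week 3 is one void against one.
- The visits do not divide cleanly. Up to three voids can mean one or two, and Protocol Version 2.0 scheduled one at Week 5, so anyone treated under it would have one there. Week 1 and predose Day 15 are the 15 mg readings, but the SAP's Day 15 window runs to Day 18 while 45 mg starts on Day 15, so some Day 15 values may follow the higher dose.
- SAP 9.3.2.1 and Appendix A note 5 already say which visits are averaged. A footnote would repeat this and change no estimate.

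The log-averaging repair also has a price. Applied throughout, it redefines the primary variable, departs from the protocol's averaging rule and gives each subject a second baseline that differs from the one used for eligibility. Applied only to the exploratory curves, it makes their Week 13 point disagree with the primary result.

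**Conclusion.** No change to the plan is needed. On the average-then-log reading, single-void visits in the Part A UPCR and UACR time courses are shifted down relative to three-void visits by about one third of the within-week log variance: 1.3% to 4.7% for CVs of 20% to 40% with independent voids, and about 0.7% to 2.4% if half the variance is shared. The size rests wholly on those assumed CVs.

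The affected outputs are exploratory and feed no dose comparison or decision rule. The primary estimate is untouched with complete voids and moves by half a percent or less if one subject has a single Week 13 void at CV 40%. The order of operations is a gap that analysts will fill in the natural way. Keeping one arithmetic baseline for eligibility, the primary and the time course is a fair trade for a small offset in the early exploratory points.

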9.3.2.2 Analyses of Exploratory Efficacy Variable

Percent change from baseline in UPCR over time during the Treatment Period: Analysis of this variable will be based on steps as described for primary analyses in Section 9.3.1.2. Subjects non-compliant with study drug will not be included in the analysis. The GMPC from baseline in UPCR, GSE (%) along with the corresponding 2-sided 80% CI and 95% CI at each post-baseline visit (Week 1, Day 15, Week 3, Week 5, Week 9, and Week 13) will be provided. The GMPC from baseline in UPCR at each post-baseline visit during the Treatment Period will also be presented in a figure.

Percent change from baseline in urine albumin-to-creatinine ratio (UACR) at Week 13: Analysis of this variable will be conducted in the same way as described for primary analyses Section 9.3.1.2. Subjects non-compliant with study drug will not be included in the analysis. The GMPC from baseline in UACR at Week 13, GSE (%) along with the corresponding 2-sided 80% CI will be provided.

Percent change from baseline in UACR over time during the Treatment Period: Analysis of this variable will be based on steps as described for primary analyses in Section 9.3.1.2. Subjects non-compliant with study drug will not be included in the analysis. The GMPC from baseline in UACR, GSE (%) along with the corresponding 2-sided 80% CI at each post-baseline visit (Week 1, Day 15, Week 3, Week 5, Week 9, and Week 13) will be provided. The GMPC from baseline in UACR at each post-baseline visit during the Treatment Period will also be presented in a figure.

Percent change from baseline in UPCR at the end of the Off-treatment Follow-up Period: Analysis of this variable will be based on steps as described for primary analyses in Section 9.3.1.2. Subjects non-compliant with study drug will not be included in the analysis. The GMPC from baseline in UPCR, GSE (%) along with the corresponding 2-sided 80% CI and 95% CI at each visit in Off-treatment Follow-up Period (Part B Week 4, Week 8, and Week 12) will be provided. The GMPC from baseline in UPCR at each post-baseline visit during the Off-treatment Period will also be presented in a figure.

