p-nCG (urine)	X				X	X	X	X	(Sections 11.6.2 and 11.6.5). This can be collected in the same sample as the urine sample for efficacy, safety, and biomarker analysis.
VX-147 dosing				X		The last dose of Treatment Period 1 will be Day 14. The first dose of Treatment Period 2 will be on Day 15 after all predose assessments are completed. The last day of dosing will occur the day before the Week 13 visit. The first dose in each period must be administered under the supervision of site medical staff or a home health nurse. Subjects will be monitored for 4 hours after receiving the first dose of each Treatment Period. (Section 9.6).			

^c Day 1 urinalysis will be for safety and biomarker assessments. Efficacy assessments will not be done.

Protocol VX19-147-101, Version 6.0

Table 3-2 Study VX19-147-101: Part A Treatment Period 1, Treatment Period 2, and Early Termination of Treatment Visit

	Treatmen	nt Period 1		Trea	atment Perio	od 2			
	Day 1 Visit	Week 1 Visit	Day 15 Visit	Week 3 Visit	Week 5 Visit	Week 9 Visit	Week 13 Visit	Early	
Event/ Assessment ^a	Window: Day 1 (±0 days)	Window: Day 8 (±1 day)	Window: Day 15 (±2 days)	Window: Day 22 (±2 days)	Window: Day 36 (±2 days)	Window: Day 64 (±2 days)	Window: Day 92 (-2 days)	Termination of Treatment Visit ^b	Comments
Adverse events			Continu	ous from signi	ng of ICF th	rough SFUV			Section 11.6.1.
Medications review			Continu	ous from signi	ing of ICF th	rough SFUV			Section 9.4.

Table 3-3 Study VX19-147-101: Postdose PK Sampling, Safety Follow-up Visit, and Part B Off-treatment Follow-up Period

Event/Assessment	Postdose PK Sampling	SFUV 28 (± 7) Days	Part B: Optional Off-treatment Follow-up	Comments
	(Approximately 48 hours after the last dose of study drug) ^a	After Last Dose of Study Drug ^b	Visits ^c (Part B Week 4 ^b , 8, and 12)	
Subject visit	X	X	X (until UPCR returns to ≥90% of baseline level)	The visit may be performed by a home health visit or in the clinic at the discretion of the investigator (Section 9.3.5). For each visit, at least 1 interaction with the subject and investigator will occur by phone, video, or in the clinic (i.e., in person, phone, or telemedicine video conference) within 1 business day after the home health visit, which can be outside the visit window. See Section 9.1.3 for details about determining the last visit for Part B.
SF-36		X		To be completed before all other study assessments (Section 11.5.3).

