7.2 Part B (Optional Off-treatment Follow-up Period)

7.2.1 Exploratory Endpoints

• Percent change from baseline in UPCR at the end of the Off-treatment Follow-up Period

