9.1.3 Part B

Participation in Part B is optional. After the last Part A Visit, subjects will be followed off-treatment at a visit scheduled every 4 weeks (\pm 2 weeks) to assess the change in proteinuria after stopping administration of VX-147 (Table 3-3). Part B visits will continue until the UPCR level reaches \geq 90% of baseline levels or 3 months after the last dose of study drug, whichever occurs first. If a subject has not achieved \geq 90% of baseline UPCR by the Part B Week 12 Visit, the Part B Week 12 Visit will be the last study visit.

Subjects will not be allowed to participate in Part B if (1) their UPCR level during Part A remained \geq 90% of baseline or (2) their UPCR level reached \geq 90% of baseline before the Part A Week 13 Visit and remained at that level through the Week 13 Visit.

The SFUV and Part B Week 4 Off-treatment Follow-up Visit may occur on the same day, provided the visit windows for both visits are met.

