12.3.3.2 Analysis of Other Variables

In all exploratory analyses of UPCR and UACR related data, the Week 5, Week 9, and Week 13 UPCR/UACR value will be calculated as the average of the available UPCR/UACR measurements (maximum 3) taken during these weeks, and the baseline value will be the average of the 3 UPCR/UACR values from the urine samples collected for this purpose during screening.

The percent change from baseline in UPCR over time during the Treatment period is an exploratory efficacy endpoint. Similar to the primary endpoint analysis, UPCR data will be log-transformed and change from baseline at each planned visit, up to Week 13, will be analyzed using the log-transformed UPCR values. The GMPC from baseline and associated 2-sided 80% CI at each planned visit will be calculated by back-transforming the corresponding estimated simple mean and CI from the log-transformed data.

Other exploratory efficacy endpoints include percent change from baseline in urinary albumin to-creatinine ratio (UACR) at Week 13, and percent change from baseline in UACR over time during the Treatment period. Analysis of these 2 endpoints will be similar to that performed for the corresponding UPCR endpoints.

Off-treatment Follow-up Period (Part B): The exploratory endpoint of percent change from baseline in UPCR at the end of the Off-treatment Follow-up Period will be analyzed similarly to the primary efficacy endpoint.

Additional details of these analyses will be provided in the SAP.

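### Part B follow-up ends when UPCR is back to at least 90% of baseline, so the Week 8 and Week 12 GMPCs describe only subjects not yet returned, and no end-of-period value is defined

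*SAP*

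**What the plan says.** - **Stopping rule.** Protocol Version 6.0, section 9.1.3: "Part B visits will continue until the UPCR level reaches" at least 90% of baseline, or until 3 months after the last dose if that comes first. Table 3-3 schedules Part B visits "until UPCR returns to ≥90% of baseline level". Only subjects still below 90% are scheduled through Week 12.
- **Entry bar.** Same section: "Subjects will not be allowed to participate in Part B if (1) their UPCR level during Part A remained" at or above 90% of baseline. Subjects who reached that level before Week 13 and stayed there are also barred.
- **Endpoint.** Protocol 7.2.1: "Percent change from baseline in UPCR at the end of the Off-treatment Follow-up Period". Protocol 12.3.3.2 says that the change "at the end of the Off-treatment Follow-up Period will be analyzed similarly to the primary efficacy endpoint" and leaves the details to the SAP.
- **Planned output.** SAP 9.3.2.2 puts under that endpoint GMPCs with GSE, 80% and 95% CIs "at each visit in Off-treatment Follow-up Period (Part B Week 4, Week 8, and Week 12) will be provided", plus a figure. The population is the Follow-up Set (SAP 8.3).
- **Missing values.** SAP 9.1 does not impute, and Appendix A note 2a treats an empty window as missing for that visit.
- **Definitions.** SAP 9.3.2.1 and Appendix A note 5 define averaged values for Weeks 5, 9 and 13 only. A Part B value is a single sample.

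**The concern.** Absence at Weeks 8 and 12 is not ordinary dropout. The protocol schedules it, and the trigger is the variable being summarised: subjects whose proteinuria rebounds first leave the later means. If a subject who is high at one visit tends to be high at the next, those who remain have lower UPCR than the whole group would have had.

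The only Part B objective is to describe proteinuria after VX-147 is stopped. A by-visit table and figure read as one population followed over time could show little rebound where the group as a whole rebounded clearly.

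Separately, the endpoint implies one value per subject at the end of that subject's follow-up, and subjects end at different visits. The SAP gives three fixed-visit summaries and no such value.

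**Working it through.** **Plan's own precision figure.** Inputs from SAP 7.2: SD 0.672 on the log scale, n = 10, two-sided 80% CI. Half-width = t(0.90, 9) × 0.672/√10 = 0.294, as stated. None is given for Part B. If five subjects were left at Week 12 (an assumption), t(0.90, 4) × 0.672/√5 = 1.533 × 0.672/2.236 = 0.461.

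**Who can be in each window.** The stopping rule removes nobody from Week 4. The SFUV urine cannot fill Weeks 8 or 12. The Week 13 visit is on Day 90 to 92 and the last dose is the day before, so the SFUV falls between 89 + 28 − 7 = Day 110 and 91 + 28 + 7 = Day 126, inside the SAP's Week 4 window (106, 134].

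**Model B: plan SD, common correlation.** Assumptions:
- Log ratios to baseline are normal with SD 0.672 at each visit.
- Geometric means are 0.5 at Week 13, then 0.6, 0.7 and 0.8 at Part B Weeks 4, 8 and 12.
- Subjects at or above 0.9 at Week 13 do not enter, approximating the entry bar.
- Visits stop after the first value at or above 0.9.

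1,000,000 draws gave:

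| Correlation | Week 12, all Part B subjects | Week 12, still attending | Week 12 gap (points) | Log bias | Week 8 gap (points) | Share attending Week 12 |
|---|---|---|---|---|---|---|
| 0 | −19.9% | −19.9% | 0 | 0 | 0 | 47% |
| 0.3 | −25.3% | −35.5% | 10.1 | 0.146 | 4.6 | 56% |
| 0.5 | −28.6% | −41.0% | 12.4 | 0.191 | 5.9 | 61% |
| 0.7 | −31.7% | −44.3% | 12.6 | 0.205 | 6.2 | 68% |

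Gaps were taken before rounding.

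The all-subject column can be checked in closed form. At correlation 0.5, the cut-off is c = ln(0.9/0.5)/0.672 = 0.875, and the mean standardised Week 13 value among entrants is −φ(c)/Φ(c) = −0.2721/0.8091 = −0.336. Each later log mean therefore shifts by 0.5 × 0.672 × (−0.336) = −0.113. Adding this to ln 0.6, ln 0.7 and ln 0.8 gives −46.4%, −37.5% and −28.5%, within 0.1 point of the simulated Week 12 value. The still-attending series is −46.4%, then −37.5 − 5.9 = −43.4%, then −41.0%. A rebound of about 18 points appears as about 5.

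Variations on Model B at Week 12, for correlations 0.3 to 0.7:
- Week 13 mean 0.4: gaps 11.0 to 15.8. Mean 0.6: gaps 9.3 to 10.7.
- Barring only subjects at or above 0.9 at both Week 9 (assumed mean 0.55) and Week 13: 11.2 to 15.0.
- Ignoring the entry bar gives 13.1 to 23.0. That range should not be used, because the protocol keeps those subjects out.

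**Model A: decay towards baseline.** Assumptions: a 50% geometric mean reduction at Week 13 (log SD 0.5, capped at a ratio of 0.85), return half-life 4 to 8 weeks with log SD 0.2 to 0.6 between subjects, and single-void log SD 0.2 to 0.4. With log SD 0.6 and void SD 0.3:

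| Half-life | Week 12, all subjects | Week 12, still attending | Last attended visit |
|---|---|---|---|
| 4 weeks | −11.3% | −17.3% | −2.3% |
| 8 weeks | −23.1% | −29.4% | −16.2% |

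Over the grid the gap is 2.1 to 3.6 points at Week 8 and 2.5 to 6.7 at Week 12, a log bias of 0.03 to 0.09 at Week 12.

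**The case against.** The best defence is that SAP 9.3.2.2 promises descriptive estimates at each visit, and the Week 12 figure correctly describes subjects still followed then. The bias exists only against a mean for all Part B subjects, which the SAP does not claim to estimate. Each returner's crossing value normally counts at its own visit. SAP 9.1 requires n, so the fall in numbers will show. The note to SAP Figure 7-1 mentions that follow-up ends on return, and a returner can be counted as having completed the study in SAP 9.2.1.

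This stands as far as it goes and makes the matter largely one of labelling. It does not remove the problem, because nothing in the planned GMPC output separates subjects who returned from those otherwise absent.

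Imprecision also dominates: the log bias is below 0.461 in both models. Model A's Week 12 attenders are less variable (SD about 0.21 to 0.47), giving half-widths of about 0.15 to 0.32 with five subjects, and its bias is smaller than those too. A wide interval still does not reveal a systematic shift.

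A reader might infer more than the documents support:
- *That the Part B analysis cannot be programmed.* The three fixed-visit outputs can be; only a per-subject end-of-period value is missing.
- *That Weeks 8 and 12 can never contain a returner.* SAP 9.1 lets unscheduled samples enter windows.
- *That an SFUV sample will displace the value that ended follow-up.* Section 9.1.3 does not say which sample decides, and the two visits may share a day.

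**Conclusion.** The point holds in a limited form. The Week 8 and Week 12 GMPCs describe subjects not returned at an earlier visit. Taken as the course of the whole Follow-up Set, they overstate residual reduction when within-subject correlation is positive, and not when it is zero. Positive correlation is plausible for repeated values divided by one shared baseline, but the documents give no figure.

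The size is uncertain: about 2.5 to 7 points at Week 12 in the decay model, and 9 to 16 points with SD 0.672 and correlations 0.3 to 0.7. The SD is stated for Week 13, not Part B; the means, half-lives and correlations are all assumed.

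The missing end-of-period definition needs no modelling assumption. It would be tempting to treat the last attended value as the correct answer. It is not: stopping on a single high reading pulls it towards rebound. In Model A at a 4-week half-life it misses the all-subject Week 12 value by 11.3 − 2.3 = 9 points, against 17.3 − 11.3 = 6 for the by-visit estimate. Part B is optional and exploratory, and the primary result is unaffected.

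**What to change.** In SAP 9.3.2.2:

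1. Label the Week 8 and Week 12 GMPCs and the figure *subjects not returned to ≥90% of baseline at an earlier visit*, with n and the number already returned.
2. Add, on the Follow-up Set, the cumulative number and proportion with UPCR at or above 90% of baseline by Weeks 4, 8 and 12. Count subjects who left before returning separately, and note that single-sample crossings overstate true return.
3. Define the end-of-period value as UPCR at the last attended nominal Part B visit. Report it beside the by-visit results, stating that stopping on one high value biases it towards rebound and that it is not a Week 12 estimate.

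A minor gain from nominal visits concerns two edge cases. The SFUV urine ("The first morning urine void will be collected and used for efficacy, safety, and biomarker analyses") shares the Week 4 window, where the value nearest Day 120 is kept. Table 3-3 allows "Week 4 Visit (Day 120 ± 2 weeks"), so a visit on Day 106 would map to Week 13 under Appendix A.

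The cost is some wording, one derivation and one small table from data already collected, with no extra visits or samples. The drawback is that items 2 and 3 lean towards rebound. In Model A at a 4-week half-life (log SD 0.6, void SD 0.3), single-sample return is 27%, 54% and 73% by Weeks 4, 8 and 12, against 19%, 43% and 63% of subjects whose underlying level is that high. They should therefore accompany the by-visit results, not replace them.
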